6.2 Procedure

There will be two arms to the protocol as detailed in section 5. The Case Report Form labelled with the appropriate subject number contains the data forms for that subject and a randomisation envelope attached inside the cover of the CRF which indicates which incubator type (standard or mOm) will be used for the baby to spend the first 24 hours in, before being switched to the alternate incubator type for a further 24 hours.

All data collected for the duration of the study will be entered in the appropriate source data (e.g. medical notes, electronic data capture systems, cleaning logs etc) and into the subject's CRF. Adverse events (AE) should be entered.

Baseline data such as length, weight, gender, core/truncal temperature (recorded at time point 0 in physiological recordings section), GA at birth, date of birth and current age of the baby will be recorded on entry to the study. Hourly observations (+/- 15 minutes) will be taken throughout the following 48 hours of incubator care, and will include temperature data displayed on the incubator, plus routine clinical observations of the baby (i.e. pulse rate, O₂ saturation and respiration rate), plus axillary temperature as per standard practice and blood pressure recorded at least once per day (See Table 1 below)

Table 1: Clinical Data Recording

Parameter	Frequency
Core/Truncal Temperature	Hourly
Pulse Rate	Hourly
Oxygen Saturation	Hourly
Respiration Rate	Hourly
Axillary Temperature	As per standard of care (usually every 2-4hrs)
Blood Pressure	As per standard of care (at least once per day)
Events (e.g. door open for feeding, care, baby removed for cuddles)	For each event record start and end time, type of activity, number of portholes/door open, any error/alarms on the incubators and any comments.

Each incubator will be individually identified by serial number for reference in CRFs, source documents (medical record/chart) and on cleaning logs. The randomisation details and the identification number of the incubators used will be recorded when the subject put into the first incubator; likewise, at the 24 hours cross-over point.

Further details about the mOm incubator can be found in the Investigator brochure (IB) filed in the ISF. For the incubator, hourly temperature readings from the digital display, time to set up, time to clean, types of cleaning performed and reasons/times when incubator opened to administer to baby's care will be recorded.

Any unanticipated Adverse Events of the baby, or of the incubator functionality, or usability (e.g. malfunction or rainout), will also be recorded on the CRF, AE log in the ISF and in the patient notes.

In addition, the views of staff will be collected through completion of a questionnaire about the baby's comfort, visibility, ease of care, usability, ease to set up, ease of

cleaning and acceptability, one for each incubator type, per staff member involved in the study activities.

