2.1.2 Risks and Management of Risk

The mOm incubator has been carefully designed to maintain a stable temperature environment for the baby.

The mOm infant incubator been manufactured under current Good Manufacturing Practice (GMP), designed and tested to provide a level of thermoregulation that meets the harmonised standards set for conventional baby incubators (BS EN 60601-2-19)^{5,6}. More information and testing results for the mOm incubator will be provided to the site clinical research team in the form of an Investigator Brochure (IB). The clinical research team will have full control and responsibility for the baby's care and can withdraw a subject from the study at any time for any reason. The risks should therefore be no more than for standard routine incubator care.

If for any reason the subject, or incubator, has any unforeseen serious adverse event whilst the baby is in the mOm incubator the subject will immediately be removed from the study and placed into standard care. Monitoring of the serious adverse event will be followed up and if the adverse event is a serious device adverse event, the study will be halted with immediate effect and only be continued when the Sponsor and Chief Investigator are confident that the issue is resolved and will not be repeated.

If there are any concerns about temperature stability (or any other matter) in any baby being nursed in the mOm incubator during the study, then standard protocols for clinical evaluation by a doctor will be followed. At the discretion of the attending clinician, the baby can be moved into a conventional (standard) incubator at any time without restriction. A spare standard incubator will always be available for this purpose.

If there are unexpected clinical incidents such as Serious Adverse Device Events (SADE) these will be reported to the Sponsor, the Research Ethics Committee (REC), Medicines and Healthcare products Regulatory Agency (MHRA), NHS Trust Research and Development as well as through the normal NHS Trust Risk reporting mechanisms (Datix).

Photographs and/or video recordings of the use of the mOm incubator may be taken during the study but will be taken in such a way so that the baby cannot be identified. The study will adhere to the principles outlined in the Declaration of Helsinki⁷, relevant Sponsor's SOPs and study- specific manuals included in the Investigator Site File (ISF) and Trial Master File (TMF), and, will follow the principles of GCP⁸.

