All data will be analysed based on intention-to-treat. Statistical analysis will focus on babies' temperature fluctuations whilst in each of the two incubators. Graphical displays of these, as well as summary statistics such as the variance of temperature throughout the two 24-hour periods will be presented. A 95% confidence interval for the size of these temperature fluctuations for each incubator type will be calculated and this measure will be used to consider whether the mOm incubator works as well as the standard one in maintaining temperature control. Secondary outcome measures will be presented similarly.

Questionnaire data will be summarised to assess usability and acceptability of the mOm incubator to the clinical research team (staff).

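### Babies may be moved out of mOm at any time, but the plan does not require the move to be logged or say how later hours count, and each way of handling them can favour mOm

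*Combined protocol and SAP*

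**What the plan says.** - **Moves.** Under section 2.1.2, if there is concern about temperature or anything else while a baby is in mOm, "the baby can be moved into a conventional (standard) incubator at any time without restriction". After an unforeseen serious adverse event in mOm, "the subject will immediately be removed from the study and placed into standard care". Nothing equivalent is said about a discretionary move. Section 6.4 does not name such a move as a reason for withdrawal. Section 5 allows the team to withdraw a baby at any time but does not require it.
- **Observations.** Section 6.2: "Hourly observations (+/- 15 minutes) will be taken throughout the following 48 hours of incubator care".
- **Incubator identity.** Section 6.2: "The randomisation details and the identification number of the incubators used will be recorded when the subject put into the first incubator". A second record of the same kind is due when the baby changes over at hour 24. The same section adds a general requirement with no time point, "Each incubator will be individually identified by serial number for reference in CRFs, source documents (medical record/chart) and on cleaning logs", and an event log: "For each event record start and end time, type of activity, number of portholes/door open, any error/alarms on the incubators and any comments". The log's examples are door opening, care and cuddles, not a change of incubator.
- **Analysis.** Section 8: "All data will be analysed based on intention-to-treat". The term is not defined for this design. Section 8 also describes fluctuations while the baby is in each incubator. It counts the required 19 of 24 readings by incubator type.
- **Sample.** Under section 5, about 40 babies are recruited and recruitment stops at 36 complete datasets.
- **Outcomes.** Unplanned moves appear in neither section 4 nor section 8.

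**The concern.** The hypothesis in section 2 is that mOm performs as well as a standard incubator. A move to the comparator because mOm did not hold a baby's temperature is direct evidence against that hypothesis, and the plan has no outcome that counts it.

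The hours after the move also have no stated owner. If they stay with mOm, the comparator's performance is mixed into mOm's result. If they do not, the baby may lack enough mOm readings to be complete, and another baby takes its place. In both cases the babies mOm served worst have less influence on the mOm result than they should.

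The secondary objective on mOm's own temperature regulation is exposed too. Incubator display readings taken after a move describe a different device.

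**Working it through.** **The plan's own figures.** With 36 babies, the two-sided 95% half-width is 1.96 × SD / √36. Section 8 gives no SD. An assumed SD of 1.0 °C gives 0.327, which matches the stated ±0.33. The completeness rule is 19/24 = 79.2%, stated as 79%. Recruiting 40 for 36 leaves room for 4 incomplete babies. These figures hold together and serve only as a scale here.

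**Route A: hours counted to the assigned period.** A move at hour h puts (24 − h)/24 of the mOm period in a standard incubator: 75% at hour 6, 50% at hour 12, 25% at hour 18. A baby moved after one hour could still be a complete mOm dataset with 23 of 24 hours spent elsewhere. Across the study there are 36 × 24 = 864 mOm-period hours. If 1 to 8 babies move at hour 12 (assumed), 12/864 = 1.4% to 96/864 = 11.1% of those hours are misattributed.

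*Effect on one moved baby's SD.* Assume an SD of 0.6 °C in mOm and 0.3 °C in standard, and a difference d in mean level before and after the move. With w = h/24, the period variance is w × 0.36 + (1 − w) × 0.09 + w(1 − w)d². The share of the excess SD that remains is (SD − 0.3)/0.3.

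| d (°C) | SD, move at hour 6 | Excess kept | SD, move at hour 8 | Excess kept |
|---|---|---|---|---|
| 0 | √0.158 = 0.40 | 32% | √0.180 = 0.42 | 41% |
| 0.5 | √0.204 = 0.45 | 51% | √0.236 = 0.49 | 62% |
| 1.0 | √0.345 = 0.59 | 96% | √0.402 = 0.63 | 111% |

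The dilution is large when the levels are equal and essentially gone at a difference of about 1 °C.

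*Effect on one moved baby's range.* This was simulated with hourly correlation from 0 to 0.8, a mean 24-hour range of 1.0 °C in standard and 1.5 °C in mOm, and no level shift (all assumed). The recorded mOm-period range is then about 1.17–1.18 after a move at hour 6, 1.29–1.32 at hour 12 and 1.40–1.42 at hour 18.

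*Effect on the mOm mean.* For moves at hour 6 the shift is (1.5 − 1.17)/36 = 0.009 °C for one baby of 36, and 8 × 0.33/36 = 0.07 °C for eight.

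**Route B: hours counted to the incubator occupied.** A baby moved at hour h has about h mOm readings, so a move before about hour 19 fails the 19-of-24 rule. Because recruitment runs until 36 complete sets exist, that baby can be replaced. A baby withdrawn at the move ends up in the same place.

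Even if the baby is kept, a range over few hours is small. In the same simulation, the range over the first 6 mOm hours averages 0.75–0.98 °C, against 1.5 °C over 24 hours. An occupied-incubator range alone would therefore not reveal the problem.

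**The case against.** A reader might infer that identity is recorded only at entry and hour 24, that a moved baby necessarily stays in, and that section 8 therefore credits standard-incubator hours to mOm. The documents do not support that chain.

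- Section 6.2 does not say that those two times are the only ones. Serial numbers in CRFs and source documents, the event log, deviation reporting (section 11.1) and source data verification might all reveal a move.
- Sections 5 and 6.4 leave withdrawal open. A move could be treated as a serious deviation, which section 6.4 makes a reason for withdrawal. Babies removed after a serious adverse event contribute no later hours.
- Section 8's wording on incubator type points towards the incubator actually occupied.

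It is also fair to say that mOm failures are partly captured already. Hypothermia and hyperthermia are recordable adverse events (section 7.1), and device events are an outcome (section 4.2.4). Moves may be few, because section 6.3 requires 24 prior hours in a standard incubator and excludes temperature instability. The study-level shift in the mean is small against ±0.33 °C in the example above. Nor is dilution of the SD guaranteed, as the 1.0 °C rows show. If fluctuation means maximum minus minimum, an excursion before the move stays in the result.

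All of this limits the claim but does not close the gap. None of the records named is required to time-stamp a change of incubator. An adverse event entry does not do so either. An analysis by occupied incubator depends on exactly that information. And reading section 8 that way leads to Route B, which has its own bias.

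**Conclusion.** The point holds as an unresolved ambiguity, not as a settled misattribution. The plan allows unrestricted moves, does not require them to be logged, does not count them, and offers two unreconciled ways of handling the hours that follow. One can blend the comparator into mOm's result. The other can remove and replace the babies who did poorly in mOm. Both can favour a conclusion of equal performance.

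The size cannot be stated, because the documents give neither a move rate nor the variability in each incubator. The figures above rest on assumed move times, numbers of moves, SDs, ranges and level differences. It would overreach to say that only about a third of the excess variability survives a move: that is near the 32% and 41% of the equal-level case and fails at larger level differences. The change should be made because it is cheap and because moves bear directly on the study question.

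**What to change.** 1. **Section 6.2:** record the date, time, reason and incubator serial number at every change of incubator.
2. **Sections 4 and 8:** add as a named outcome the number and timing of unplanned moves out of each incubator type for temperature or device reasons. Report it for all randomised babies and read it alongside the temperature result.
3. **Section 8:** define intention-to-treat for this cross-over and keep the as-randomised analysis. Add an analysis that uses only readings taken in the incubator actually occupied. For the device-regulation objective, take mOm display readings only from mOm.
4. **Sections 5 and 8:** keep moved babies in the analysis. Do not exclude or replace them as incomplete because of the move.

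Sections 2.1.2, 5 and 6.4 should also be reconciled so that it is clear whether a discretionary move ends participation. Which it should be is for the clinical team, and their freedom to move a baby is unchanged.

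The cost is one CRF line and one extra analysis. Moved babies will have fewer mOm readings in the occupied-incubator analysis, where a short window also shrinks the range. That is why the move count has to be read beside it.

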6.3 Inclusion / Exclusion Criteria

6.3.1 Inclusion criteria

The subject must satisfy all the following criteria to be eligible for the study:

- Parent/legal guardian is willing and able to give informed written consent for participation of their baby in the study.
- Parent/legal guardian is aged 16 years or above.
- Subject has spent at least a day (24 hours) in a standard incubator.
- Subject considered clinically stable from a cardio-respiratory point of view.
- Subject requires incubator care but does not require additional humidification.
- Subject requires incubator care for at least 48 hours.
- Subject is at least 30 weeks gestational age.
- Subject is less than or equal to 6kg in weight.

6.3.2 Exclusion Criteria

The subject may not enter the study if, in the opinion of the Investigator, or delegatee taking consent, ANY of the following apply:

- Parent/legal guardian with learning disabilities or mental illness and is considered unable to give informed consent.
- Parent/legal guardian is a prisoner and young offender.
- Parent/legal guardian is considered to have a particularly dependent relationship with the investigator(s).
- Parent/legal guardian is deemed to belong to a vulnerable group.
- Subject has major congenital abnormalities.
- Subject has temperature instability, defined as being outside of a normal range based on each infant's individual characteristics.
- Attending clinician and/or nursing concern regarding clinical stability of the infant (e.g. infection suspected).

6.4 Withdrawal of Patients from the study

All subjects (via their parent/legal guardian) are free to withdraw from the study at any time for any reason without their standard of care being affected. If a patient is withdrawn before the completion of this study, the reason(s) for withdrawal will be documented where possible.

Withdrawal of a subject by a member of the clinical research team will occur for any of the following reasons:

- An unanticipated serious adverse event (e.g. SAE or SADE) which requires immediate change to alternative treatment.
- A protocol violation (*i.e.* violation of the inclusion/exclusion criteria during screening period or serious deviation from the clinical investigation plan, or guidelines during the study which may affect the integrity of the study or the patient's well-being).

7. ADVERSE EVENTS

7.1 Adverse event (AE)

Any undesirable clinical occurrence in a subject, whether considered to be procedure related or not, that includes a clinical sign or symptom. Typical AEs which should be recorded include but are not limited to: skin injury or infection, pressure sores, hyperthermia, hypothermia, apnea and bradycardia. AEs also include Adverse Device Events (ADEs). ADEs are any undesirable device related event, whether clinically relevant to the subject or not. Typical device ADEs which should be recorded include but are not limited to: rainout, practical access issues, degradation of part of the incubator, inadvertent displacement of lines thought to be due to the design of the incubator.

AEs will be recorded from the time the subject has been enrolled and placed in the first incubator type until the end of their participation in the study (*i.e.* after 48 hours incubation is complete), unless a device related adverse event is on-going in which case it will be monitored until resolved. All AEs should be recorded in the patient notes, the CRF and on the Adverse Event log in the ISF.

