5. STUDY DESIGN

The study has a prospective, multi-centre, randomised controlled, cross-over design. There will be two arms to the research. The first arm will consist of mOm incubator

care for 24 hours, followed by a further 24 hours where the subject is transferred for care to a standard incubator. The second arm will consist of 24 hours care in a standard incubator followed by 24 hours care in a mOm incubator. The care of the baby (subject) is mostly unchanged from standard incubator care, but observations may be recorded more frequently (*i.e.* hourly) for incubator displayed temperatures and some other physiological measures of clinical stability than would normally be collected in routine care for this type of clinically stable baby of at least 30 weeks GA (normally every three hours) (See Table 1). No additional blood tests or any other invasive testing or monitoring are required. The clinical research team will have full control and responsibility for the baby's care, with the ability to withdraw the baby from the study at any time for any reason if they feel the baby is clinically unstable or is adversely affected by their environment. The order of incubator type in which the baby is cared for (*i.e.* which arm of the study) before being crossed over to the alternative incubator type will be assigned at random at the point of written consent being gained and the subject therefore having been officially recruited.

Babies that are considered clinically stable from a cardio-respiratory point of view but require at least 48 hours incubator care but not requiring additional humidification will be recruited to the study from the Neonatal Unit. In practice, this will mostly be babies weighing less than approximately 1400g at 30 weeks, although some term babies may also be eligible for the study if they are being nursed in an incubator for clinical reasons.

The aim is to collect 36 completed data sets for analysis; to achieve this approximately 40 babies will be recruited; recruitment will be stopped once 36 completed data sets are available. The target is to complete recruitment within a nine-month period.

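### No collection of new adverse events is planned after 48 hours, so babies who have the mOm incubator second have no adverse event window after mOm, against 24 hours for those who have it first

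*Combined protocol and SAP*

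**What the plan says.** Collection starts at time 0: "AEs will be recorded from the time the subject has been enrolled and placed in the first incubator type" (section 7.1). It runs "until the end of their participation in the study (*i.e.* after 48 hours incubation is complete), unless a device related adverse event is on-going". An event of that kind is followed until it resolves, and this is the only exception that 7.1 gives. Section 7.4 requires the patient's notes and the AE log to cover events that occur during participation. The study summary gives participation as 48 hours per subject.

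Section 5 sets the two orders. The relevant one here is: "The second arm will consist of 24 hours care in a standard incubator followed by 24 hours care in a mOm incubator". For these babies the study ends when the mOm period ends.

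Section 2.1.2 deals with an unforeseen serious event in mOm: "the subject will immediately be removed from the study and placed into standard care". It adds: "Monitoring of the serious adverse event will be followed up". Section 6.4 asks for the reason for a withdrawal to be documented and says nothing about AE collection afterwards.

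Section 7.1 also tells sites what to look for: "Typical AEs which should be recorded include but are not limited to: skin injury or infection, pressure sores", followed by disturbances of temperature, breathing and heart rate. Incubator-related adverse events are a secondary objective (section 3.2), and device events, serious ones included, are a secondary outcome (section 4.2.4).

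**The concern.** The AE window is tied to time in the study and not to time since exposure to the device under test. In a two-period cross-over this gives the two orders different follow-up after mOm. Some of the events that 7.1 asks sites to record, such as skin injury and pressure sores, need not be visible by the last hour in the incubator. If one first appears after a baby has finished mOm as the second period, no planned step would record it.

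The safety summary for mOm is at stake. An absence of late events could mean that none occurred, or that half the babies were not followed for them. Section 2.1.2 halts the study after a serious device event, and an event that is never collected cannot prompt that halt.

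Attribution is a related difficulty. A delayed event can first appear in the other incubator's period, and sections 7.1, 7.4 and 8 give no rule for assigning an event to a period.

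**Working it through.** The plan gives no figure for AE follow-up. Its one precision figure, ±0.33 degrees with 36 babies in section 8, concerns the primary outcome. It reproduces as 1.96 × 1.0/√36 = 0.327 if the SD is 1.0 degree (assumed, not stated), and has no bearing on this point.

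**Step 1: windows after mOm.** Inputs: collection ends at 48 hours (7.1); two periods of 24 hours (section 5).
- mOm first: mOm ends at hour 24, so 48 − 24 = 24 hours remain.
- mOm second: mOm ends at hour 48, so 48 − 48 = 0 hours remain.

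This step needs no assumption about latency.

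**Step 2: number of babies.** The allocation ratio is not stated. At 1:1 (assumed), 36/2 = 18 completers have no post-mOm window. The other 18 supply 18 × 24 = 432 baby-hours. With simple, unblocked randomisation the 95% range for the number having mOm second is 12 to 24 of 36.

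**Step 3: do the exceptions fill the gap?** The exception in 7.1 needs an event that is already on-going. The follow-up in 2.1.2 concerns the serious event that caused removal. Neither picks up an event that starts later.

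**Step 4: what zero events would show.** The one-sided 95% upper bound is 1 − 0.05^(1/n). For n = 36 it is 8.0%. For the n = 18 with any post-mOm window it is 15.3%.

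**Step 5: illustration by lag.** Suppose an event appears L hours after the mOm exposure that caused it, with exposure uniform over the 24 hours. Capture is min(1, (48 − L)/24) for mOm first and (24 − L)/24 for mOm second, neither below 0.

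| Assumed lag L | mOm first | mOm second |
|---|---|---|
| 6 h | 100% | 75% |
| 12 h | 100% | 50% |
| 24 h | 100% | 0% |
| 36 h | 50% | 0% |
| 48 h or more | 0% | 0% |

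With an exponential lag of mean m, capture is the average of 1 − exp(−(W − u)/m) over u from 0 to 24. W is the time from the start of mOm to the end of collection: 48 for mOm first and 24 for mOm second. Extending collection by 24 hours makes these 72 and 48.

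| Mean lag | Now: first / second | With 24 h added: first / second |
|---|---|---|
| 24 h | 77% / 37% | 91% / 77% |
| 48 h | 52% / 21% | 71% / 52% |

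For m = 24 the current values are 1 − (e⁻¹ − e⁻²) = 0.767 and e⁻¹ = 0.368. With 24 hours added, mOm first becomes 1 − (e⁻² − e⁻³) = 0.914. The extension raises both orders but does not make them equal.

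**The case against.** The plan does not abandon babies at 48 hours. On-going device-related events are monitored until resolved, the serious event behind a removal is followed up, and clinical care continues. Section 7.4 also requires serious events to be reported within 24 hours of the site learning of them, so a late one that came to notice might still be reported. Many of the listed events, such as apnoea, bradycardia, rainout and line displacement, would mostly be evident while the baby is inside. AEs are a secondary outcome, the primary analysis is unaffected, and length of follow-up is a design choice. All of this stands, and it limits the point to new-onset or late-recognised events. It does not supply a step that would look for them.

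A reader might infer four stronger things that the documents do not support.
- **That mOm-second or withdrawn babies get no observation at all after mOm.** The two exceptions contradict this.
- **That collection formally closes at withdrawal.** This is the likely reading, but it is an inference: 7.1 glosses the end of participation as 48 hours completed and 6.4 is silent. A clinician's move of a baby to a standard incubator under 2.1.2 is not expressly a withdrawal.
- **That the protocol names infection, skin injury and pressure sores as risks of mOm.** They are listed in 7.1 as typical AEs to record in either incubator. Section 2.1.2 names none of them, and the wording may mean skin infection only.
- **That delayed mOm harm will be counted against the comparator.** The shift runs both ways. Delayed effects of the standard incubator can appear in a later mOm period, and section 6.3.1 requires at least 24 hours in a standard incubator before entry, so this applies to mOm-first babies too. Table 3 grades relationship to device, comparator or procedures, and section 6.2 records which incubator was used at the start and at cross-over. A dated event can therefore largely be placed.

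**Conclusion.** The point holds for new-onset events. None are planned to be collected after 48 hours, and none are stated to be collected after withdrawal. Post-mOm collection is 24 hours for mOm-first babies and 0 hours for mOm-second babies, who number about 18 of 36 if allocation is 1:1. The 24-against-0 difference follows directly from sections 5 and 7.1. The capture percentages rest on assumed latencies and only illustrate how the gap depends on lag: it is small at 6 hours, complete for mOm-second babies at 24 hours, and shared by both orders from 48 hours. The documents cannot say how many events would be missed or in which direction the comparison would move. This is a cheap improvement to the secondary safety outcome and does not affect the primary analysis.

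**What to change.** In 7.1 and 7.4, extend collection of new AEs and SAEs to a fixed time of at least 24 hours after the last hour in a study incubator, by one review of routine notes. Apply it to both orders, and to withdrawn babies where consent allows, so that every baby has at least 24 hours of AE collection after mOm. State explicitly what is collected after withdrawal. Keep the existing rule that on-going device-related events are monitored until resolved.

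For each AE, record the onset time, the incubator in use at onset and the incubator used in the preceding 24 hours. Report mOm AEs by order, because post-mOm time will still be longer in mOm-first babies (48 against 24 hours if the extension is 24 hours).

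The cost is a few minutes of chart review per baby by existing research staff, and small changes to the CRF and to the information sheet, since participation is stated as 48 hours. No extra procedure is needed. Notes may be limited for babies transferred elsewhere.
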